**8 INVESTIGATIONAL PLAN**

**8.1 VISIT SCHEDULE**

All study agent administrations at the study site will be done under the direct supervision of the study personnel for documentation of precise administration times. In case a visit is delayed beyond the window detailed in [Section 15.1, Schedule of Events Table](#), the delayed visit should be scheduled as soon as possible and documented with the actual date and the reason for the delayed visit. The next visit should still take place at the time it was originally scheduled in this treatment course. Any delays in visit dates, outside of the defined criteria in the Schedule of Events Table, will be reported as a protocol deviation.

**8.2 VISIT PROCEDURES**

The investigations as outlined in [Section 15.1, Schedule of Events Table](#) will be performed at the respective visits as described in detail in the following sections.

## 8.2.1 SCREENING AND RUN-IN PERIOD

The screening period (Visit 1), i.e. the phase after informed consent and before the first administration of the study agent, may be as long as 6 days (day -7 to -2). However, a pretrial fundus photography/FA examination performed within 14 days prior to Visit 1 can be used as the screening ophthalmologic examination. In special cases where it is not logistically possible to meet the protocol defined screening period, the screening can be extended by an additional 7 days (day -14) without repeating the screening assessment.

The medical history and medication history within 3 months prior to Visit 1, as well as baseline condition of the subject, will be captured in the eCRF.

### 8.2.1.1 Visit 1

At Visit 1, the following procedures and assessments are performed:

- Signing of all applicable Informed Consents
- Potential study subject eligibility based on all study-specific inclusion and exclusion criteria (see [Sections 5.1](#) and [5.2](#))
- Demographics and medical history
- All ophthalmological evaluations: BCVA, SD-OCT, fundus photography/FA, slit lamp, and IOP (see [Sections 7.1](#) and [7.2.5](#))
- Vital signs, physical examination, safety laboratory tests, **Poland only**: serum pregnancy test (in women of childbearing potential), and 12-lead ECG, (see [Sections 7.2.2](#), [7.2.3](#) and [7.2.4](#))
- Review of concomitant medications (see [Sections 6.3](#) and [6.4](#))
- AE reporting and evaluation according to [Section 7.2.1](#)

## 8.2.2 TREATMENT PERIOD

All ophthalmic examinations and other assessments will be performed before intake of the study agent on the respective day. The examinations of each visit are specified in [Section 15.1, Schedule of Events Table](#). In addition, please see [Section 17.2.1, Table of Pharmacokinetic, Biomarker, and Pharmacogenomic Sampling](#) for detailed information regarding these evaluations.

### 8.2.2.1 Visit 2

At Visit 2, the following procedures and assessments are performed:

- Pharmacokinetic and biomarker samples are taken (see [Sections 7.2.6](#) and [7.2.8](#))
- Pharmacogenomic samples are taken (see [Section 7.2.7](#))
- Specified ophthalmological assessments: BCVA, SD-OCT, slit lamp, and IOP
- Vital signs, physical examination, safety laboratory tests, and **Poland only**: serum pregnancy test (in women of childbearing potential)
- Review of concomitant medications

- AE reporting and evaluation
- Study agent administration training and study agent dispensing/administration
- Study agent accountability

#### 8.2.2.2 Visit 3

At Visit 3, the following procedures and assessments are performed:

- Pharmacokinetic samples are taken
- Specified ophthalmological assessments: BCVA, SD-OCT, slit lamp, and IOP
- Vital signs, safety laboratory tests, and 12-lead ECG
- Review of concomitant medications
- AE reporting and evaluation
- Study agent dispensing/administration
- Study agent accountability

#### 8.2.2.3 Visit 4

At Visit 4, the following procedures and assessments are performed:

- Pharmacokinetic samples are taken
- Specified ophthalmological assessments: BCVA, SD-OCT, slit lamp, and IOP
- Vital signs, physical examination and safety laboratory tests
- Review of concomitant medications
- AE reporting and evaluation
- Study agent dispensing/administration
- Study agent accountability

#### 8.2.2.4 Visit 5

At Visit 5, the following procedures and assessments are performed:

- Pharmacokinetic samples are taken
- Specified ophthalmological assessments: BCVA, SD-OCT, slit lamp, and IOP
- Vital signs and safety laboratory tests
- Review of concomitant medications
- AE reporting and evaluation
- Study agent dispensing/administration
- Study agent accountability

### 8.2.2.5 Visit 6

At Visit 6, the following procedures and assessments are performed:

- Pharmacokinetic and biomarker samples are taken
- Specified ophthalmological assessments: BCVA, SD-OCT, slit-lamp, and IOP
- Vital signs, physical examination, safety laboratory tests, and 12-lead ECG
- Review of concomitant medications
- AE reporting and evaluation
- Study agent dispensing/administration
- Study agent accountability

### 8.2.2.6 Visit 7

At Visit 7, the following procedures and assessments are performed:

- Pharmacokinetic samples are taken
- Specified ophthalmological assessments: BCVA, SD-OCT, slit lamp, and IOP
- Vital signs and safety laboratory tests
- Review of concomitant medications
- AE reporting and evaluation
- Study agent dispensing/administration
- Study agent accountability

---

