- Patients with a clinically relevant abnormal screening hematology, blood chemistry, or urinalysis, if the abnormality defines a significant disease as defined in other exclusion criteria (e.g., aspartate aminotransferase (AST) or alanine aminotransferase (ALT) greater than 2.0-fold the upper limit of normal at screening; total bilirubin or prothrombin time (INR) > 1.5 times the upper limit of normal at screening). Laboratory testing may be repeated once during the screening phase
- Patients with impaired renal function defined as calculated glomerular filtration rate (GFR) < 30 mL/min
- Significant alcohol or drug abuse within past 2 years
- Based on electrocardiogram (ECG) reading, patients with a risk of prolonged QT interval effects including:
  - A marked baseline prolongation of QTc (using Bazett's formula:  $\geq 430$  ms in men and  $\geq 450$  ms in women) with confirmation on a repeat ECG)
  - A history of additional risk factors for Torsade de Pointes (TdP) (e.g., heart failure, hypokalemia, family, history of Long QT Syndrome, etc.)
  - The use of concomitant medications known to prolong the QT/QTc interval
- Significant disease or other medical conditions (as determined by medical history, examination, and clinical investigations at screening) that may, in the opinion of the investigator, result in the any of the following:
  - Put the patient at risk because of participation in the study
  - Influence the results of the study
  - Cause concern regarding the patient's ability to participate in the study
- Patients with malignancy for which the patient has undergone resection, radiation or chemotherapy within past 5 years; patients with treated basal cell carcinoma or fully cured squamous cell carcinoma are allowed

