**6.1.4 DOSING AND ADMINISTRATION**

The study agent will be self-administered orally twice daily for a total daily dose of 800 mg. Training on study agent administration will be conducted prior to initial study agent administration (at Visit 2) under the supervision of study personnel. All study agent administrations at the study site will be done under the direct supervision of the study personnel for documentation of precise administration times.

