### 7.2.1.2.7 Adverse Events of Special Interest

The following are considered adverse events of special interest (AESI):

- Hepatic injury defined by the following alterations of liver parameters:  
For subjects with normal liver function at baseline an elevation of AST and/or ALT  $\geq$  3-fold ULN combined with an elevation of total bilirubin  $\geq$  2-fold upper limit of normal (ULN) measured in the same blood draw sample. Subjects showing these lab abnormalities need to be followed up according to [Section 17.1.2](#).
- Abrupt decrease ( $>$  15 letters lost from baseline) of BCVA
- QTc prolongation ( $>$  +50 ms from baseline and  $>$  450 ms)

Protocol-specific AESIs are to be reported in an expedited manner similar to SAEs even if they do not meet any of the criteria for an SAE (see [Section 7.2.1.2.2](#)).

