**15 SCHEDULE OF EVENTS**

**15.1 SCHEDULE OF EVENTS TABLE**

Visit Number Day Time Window (days)	Screening	Treatment Period							Follow-Up		
	1 -7 to -2	2 1	3 8 ±1	4 15 ±1	5 22 ±1	6 29 ±1	7 36 ±1	8/EOT  43 ±1	9/FU 50 ±1	10/FU 57 ±1	Phone/FU 71 ±1
Informed Consent 	X										
Informed Consent for Pharmacogenomics 	X										
Demographics	X										
Medical history	X										
Inclusion/exclusion criteria 	X	X									
Physical examination	X	X		X		X		X 		X	
Vital signs (seated)	X	X	X	X	X	X	X	X 	X	X	
Pregnancy test (as applicable) 	X	X						X			
Laboratory tests	X	X	X	X	X	X	X	X 	X	X	
12-lead ECG	X		X			X		X 			
SD-OCT	X	X	X	X	X	X	X	X 	X	X	
Fundus photography/FA	X							X 			
Visual acuity	X	X	X	X	X	X	X	X 	X	X	
Slit lamp	X	X	X	X	X	X	X	X 	X	X	
IOP	X	X	X	X	X	X	X	X 	X	X	
Administration of study agent 		X	X	X	X	X	X	X 			
Dispense study agent		X	X	X	X	X	X				
Study agent accountability		X	X	X	X	X	X	X 			
Pharmacokinetics blood sample (for plasma extraction)		X 	X 	X 	X 	X 	X 	X 	X		
Biomarker plasma aliquots		X 				X 		X 	X 		
Pharmacogenomics blood sample		X 									
Adverse events 	X	X	X	X	X	X	X	X 	X	X	X
Concomitant/current medications 	X	X	X	X	X	X	X	X 	X	X	X
Trial completion											X

- All subjects must sign an informed consent consistent with ICH-GCP guidelines prior to any trial related procedures, which includes medication washouts and restrictions.
- Informed consents must be obtained for pharmacogenomic sampling [REDACTED]. Pharmacogenomics sampling will be performed at enrollment/baseline (Visit 2). [REDACTED].
- A preliminary check of inclusion/exclusion criteria will be performed at screening (Visit 1) after obtaining informed consents.
- Study agent will be self-administered in the clinic under supervision of study personnel during every visit of the treatment period (Visits 2-8) following all safety and ophthalmic assessments. Training on study agent administration will be conducted prior to the initial study agent administration at Visit 2.

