## 17.2 PHARMACOKINETIC, BIOMARKER, AND PHARMACOGENOMIC SAMPLING

### 17.2.1 TABLE OF PHARMACOKINETIC (PK), BIOMARKER, AND PHARMACOGENOMIC (PGX) SAMPLING

Visit	Day	Time Point	Time for Database Setup	PK Blood	Extra Biomarker Aliquot from PK Blood Sample	PGX Blood
2	1	Prior to (i.e., within 15 min before study agent administration)	-0:15 h	X	X	X
		0:00	0:00 h	Study agent administration		
		0:15 ± 5 minutes	0:15 h	X		
		0:30 ± 5 minutes	0:30 h	X		
		1:30 ± 20 minutes	1:30 h	X	X	
		3:00 or later (preferably at the end of all visit procedures)	3:00 h	X		
3	8 (±1)	-00:15 min (i.e., within 15 min before study agent administration)	167:45 h	X		
4	15 (±1)	-00:15 min (i.e., within 15 min before study agent administration)	335:45 h	X		

5	22 (±1)	-00:15 min (i.e., within 15 min before study agent administration)	503:45 h	X		
6	29 (±1)	-00:15 min (i.e., within 15 min before study agent administration)	671:45 h	X	X	
7	36 (±1)	-00:15 min (i.e., within 15 min before study agent administration)	839:45 h	X		
8	43 (±1)	-00:15 min (i.e., within 15 min before study agent administration)	1,007:45 h	X	X	
9	50 (±1)	Any time during visit – preferably at the end of all visit procedures	1,179:00 h	X	X	

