16.5 Electrocardiogram (ECG)

ECGs will be measured at screening Visit 1, Visit 3, Visit 6, and Visit 8/EOT, and graded as normal or abnormal. Abnormal findings or changes from baseline will be further classified as not clinically significant (NCS) or clinically significant (CS). In the event abnormal ECG results requires additional follow up, ECGs may be performed at unscheduled visits or at a study visit that an ECG is not required per protocol. ECG data performed outside of the protocol specified time points will be captured in the EDC on an "Unscheduled Visit" eCRF and mapped to the nearest scheduled visit as defined in [Section 9.3](#). ECG grades and shift from baseline will be summarized with counts and percentages for each visit for the Safety set. All clinically significant findings will be recorded as AEs in the eCRF and followed until resolution. Once resolved, the AE eCRF page(s) will be updated. A subject listing of the ECG results will also be produced.

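### All scheduled on-treatment ECGs precede the day's dose, so they cannot systematically detect a QTc rise near peak concentration

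*Protocol*

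**What the plan says.** Two protocol rules fix the order of events on a treatment day. Section 8.2.2 says: "All ophthalmic examinations and other assessments will be performed before intake of the study agent on the respective day". Footnote 4 to the schedule of events (15.1) says that the supervised clinic dose is taken "during every visit of the treatment period (Visits 2-8) following all safety and ophthalmic assessments". SAP 4.2 repeats the footnote.

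SAP 16.5 gives the ECG visits: "ECGs will be measured at screening Visit 1, Visit 3, Visit 6, and Visit 8/EOT, and graded as normal or abnormal". The protocol schedule agrees, and Visit 2 has no ECG. Protocol 7.2.3 describes how the tracing is made and refers to the schedule for time points. It gives no time relative to dose.

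Post-dose PK samples are taken at Visit 2 only. The table in 17.2.1 sets them at 0:15, 0:30, "1:30 ± 20 minutes" and 3:00 h or later. From Visit 3 to Visit 8 the only PK sample is pre-dose.

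The protocol monitors QT explicitly. Section 5.2 excludes patients with QT risk factors. Section 7.2.1.2.7 makes "QTc prolongation", defined as more than 50 ms above baseline and above 450 ms, one of three AESIs that are reported in an expedited manner.

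**The concern.** If a drug lengthens QTc in proportion to its concentration, the effect is largest near peak and smallest just before the next dose. A schedule that records ECGs only before the dose samples the weakest point of that profile. The QTc AESI might then fail to trigger because of when the tracing was made.

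The other two AESIs do not share this weakness to the same degree. They rest on liver tests and visual acuity, which are measured at every clinic visit, whereas QTc has three scheduled on-treatment tracings, all at the same point of the dosing cycle. Safety is the only secondary endpoint, accumulated adverse event data inform the decision to stop recruitment (10.4.4; SAP 18), and the trial is meant to support longer studies if the results are favourable (2.2). A finding of no QTc AESI could be read as more reassuring than the ECG timing allows.

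**Working it through.** The plan gives no figure to reproduce on this point. The check sets the ECG visits against the dosing order and the PK clock, then illustrates the possible size.

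**1. Visits side by side** (Protocol 15.1 and 17.2.1)

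| Visit | Day | ECG | Post-dose PK | Position of ECG |
|---|---|---|---|---|
| 1 | -7 to -2 | yes | none | before any drug |
| 2 | 1 | no | four samples | no ECG |
| 3 | 8 | yes | none | before the day's dose |
| 6 | 29 | yes | none | before the day's dose |
| 8 | 43 | yes | none | before the day's dose |

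Scheduled on-treatment ECGs: 3 visits x 30 subjects = 90. Number after the day's dose: 0. No scheduled ECG shares a visit with a post-dose PK sample. Visit 8 is described in 8.2.3, outside 8.2.2, but footnote 4 names Visits 2 to 8 and so covers it.

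**2. Time since the previous dose**

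Protocol 6.1.4 states: "The study agent will be self-administered orally twice daily for a total daily dose of 800 mg". SAP 13.1 describes a morning and an evening dose. A 12-hour interval is an inference from this. The nominal pre-dose PK times, modulo 12 h, are:

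- Visit 3: 167.75 - 13 x 12 = 11.75 h
- Visit 6: 671.75 - 55 x 12 = 11.75 h
- Visit 8: 1,007.75 - 83 x 12 = 11.75 h

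The ECG has no clock time of its own. Because it also precedes the dose, it falls at about the same point.

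**3. Illustration of size**

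The documents give neither a half-life nor a time of peak. Assume 12-hourly dosing, a peak at 1.5 h, exponential decline after it, and a QTc effect proportional to concentration with no delay. Then trough/peak = 2^(-(12 - 1.5)/half-life) = 2^(-10.5/half-life).

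| Half-life (h) | Trough/peak | 60 ms at peak appears at trough as | Peak rise needed for +50 ms at trough |
|---|---|---|---|
| 3 | 0.088 | 5.3 ms | 566 ms |
| 6 | 0.297 | 17.8 ms | 168 ms |
| 12 | 0.545 | 32.7 ms | 92 ms |
| 24 | 0.738 | 44.3 ms | 68 ms |
| 48 | 0.859 | 51.6 ms | 58 ms |

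The 60 ms is chosen only because it exceeds the 50 ms change limit. The illustration leaves aside the second condition, an absolute QTc above 450 ms.

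**4. Sensitivity**

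With the ECG at 11.75 h and a peak anywhere from 0.5 to 3 h, the ratio is 7-13%, 27-36%, 52-60% and 72-78% for half-lives of 3, 6, 12 and 24 h. A 60 ms peak rise reaches 50 ms at trough when 2^(-10.5/half-life) = 50/60, which gives a half-life of 10.5/log2(1.2), or about 40 h. At a half-life of 24 h, a 70 ms peak rise would appear as 51.7 ms. The result therefore depends heavily on the assumed inputs.

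**The case against.** Several points on the other side are sound.

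- **Unscheduled ECGs exist.** Protocol 7.2.3 lets the investigator take additional ECGs for safety reasons, and SAP 16.5 provides for follow-up of abnormal tracings. A reader might infer that QTc is never checked near peak, or that a subject with a peak effect would necessarily go undetected. The documents support neither, since an unscheduled ECG could fall at any time and adverse events are reviewed at every visit. These ECGs are discretionary or triggered, however, so they give no systematic data near peak.
- **No visible text says that the drug prolongs QT.** A reader might infer a known drug effect from the exclusions and the AESI. Section 2.3.1 names chiefly procedural risks, the exclusions concern risk in the patient, and the AESI may be a precaution. Earlier ECG data at peak exposure may sit in the redacted background or unpublished references, and would bear on how much post-dose tracings are needed here.
- **The figures are illustrative.** A reader might infer that any peak rise above 50 ms would be hidden. That fails for half-lives above about 40 h at 60 ms, and for larger rises at shorter half-lives. A delayed effect, or one driven by metabolites (which 7.2.6.3 plans to measure if feasible), would also change the picture.
- **The plan promises no cardiac safety conclusion.** Safety analysis is descriptive, ECG is absent from the endpoint lists in 10.4.2 and SAP 16, and SAP 16.5 summarises only normal/abnormal grades and shifts.
- **Pre-dose ECGs have some value.** They are close in time to the pre-dose PK samples, and moving all three would lose that pairing.

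These points limit the wording and the remedy. They do not alter the fact that following the schedule exactly yields no post-dose tracing.

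**Conclusion.** The point holds for protocol-scheduled ECGs. None of the three on-treatment ECG visits (0 of 90 planned tracings) has its ECG after the day's dose, and Visit 2, the only visit with post-dose PK, has no ECG. The scheduled tracings cannot systematically detect a concentration-related QTc rise near peak, although QTc prolongation is an expedited AESI.

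The order of ECG and dose is certain from the text. Its placement at about the end of the dosing interval rests on an inferred 12-hour interval. How much it matters cannot be computed from the documents. Under the stated assumptions, trough would be about 9% to 74% of peak for half-lives of 3 to 24 h, and the gap shrinks with a longer half-life or a delayed effect.

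This is an avoidable blind spot in safety monitoring that is cheap to narrow. It does not affect the BCVA analysis and is not evidence of a QT effect.

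**What to change.** - **Retime two ECGs.** In Protocol 8.2.2 and footnote 4 of 15.1, and in the SAP 4.2 copy of the footnote, exempt the 12-lead ECG at Visits 3 and 6 from the rule that assessments precede the dose. Record it after the supervised dose, in a window the sponsor sets from its own PK data, for example one that matches a Visit 2 PK time. Record time since dose with each tracing. About 60 of the 90 planned tracings (2 visits x 30 subjects) would then be post-dose.
- **Keep the Visit 8 ECG pre-dose.** This retains one tracing timed with a pre-dose PK sample. The screening ECG remains the drug-free baseline.
- **Reconcile Visit 8.** The 15.1 schedule marks study-agent administration at Visit 8 and 17.2.1 times its PK sample before a dose, but the procedures in 8.2.3.1 list no administration. The passages need to agree.
- **If the timing is left as it is,** state in the report that scheduled ECGs were pre-dose and that the absence of QTc AESIs does not exclude an effect near peak.

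The cost is a wording change and a longer stay at two visits (about 1.5 h each if the 1:30 h time were used). It also leaves one scheduled trough tracing per subject where there were three, and no same-time PK sample for the two post-dose ECGs unless one is added. The number of ECGs does not change.

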## 8.2.3 END OF TREATMENT

All end of treatment (EOT) study-related procedures will be conducted at the conclusion of 6 weeks of treatment on Day 43 ±1. However, for subjects who withdraw consent from the study, no study procedures will be done thereafter. For subjects that withdraw from the study agent, EOT procedures and follow-up visits are to occur as per the protocol. Excluding cases of medical emergency, but prior to the discontinuation of a subject from the clinical study for disease worsening, the study investigator should discuss each case of discontinuation with the sponsor.

### 8.2.3.1 Visit 8

At Visit 8, the following procedures and assessments are performed:

- Pharmacokinetic and biomarker samples are taken
- All ophthalmological assessments: BCVA, SD-OCT, fundus photography/FA, slit lamp, and IOP
- Vital signs, physical examination, safety laboratory tests, **Poland only**: serum pregnancy test (in women of childbearing potential), and 12-lead ECG

- Review of concomitant medications
- AE reporting and evaluation

---

#### 8.2.4 FOLLOW-UP VISITS

Follow-up visits will be performed after Visit 8 for all subjects who had at least one dose of trial treatment. Follow-up visits will not be performed if:

- The subject is lost to follow-up
- The subject withdraws consent from the study
- The investigator and sponsor agree not to pursue further follow-up visits with the subject
- The subject dies

In these cases, the trial completion page of the eCRF must be filled out.

##### 8.2.4.1 Visit 9

At Visit 9, the following procedures and assessments are performed:

- Pharmacokinetic and biomarker samples are taken
- Specified ophthalmological assessments: BCVA, SD-OCT, slit lamp, and IOP
- Vital signs and safety laboratory tests
- Review of concomitant medications
- AE reporting and evaluation

##### 8.2.4.2 Visit 10

At Visit 10, the following procedures and assessments are performed:

- Specified ophthalmological assessments: BCVA, SD-OCT, slit lamp, and IOP
- Vital signs, physical examination, and safety laboratory tests
- Review of current medications
- AE reporting and evaluation

##### 8.2.4.3 Safety Follow-up: Documented Phone Call

At Day 71 (28 days after end of treatment), the following assessments are performed by phone:

- Review of current medications
- AE reporting and evaluation

In addition, the Trial Completion page must be finalized and entered in the eCRF.

